4.6.2.3 Dose Modification Criteria for FOLFOX

Recommended dose modifications of FOLFOX are provided in Table 4.6.2.3-1 and Table 4.6.2.3-2.

Table 4.6.2.3-1: Recommended Dose Modifications of FOLFOX

Dame	Charting Dage	Dose Modification		
Drug	Starting Dose	Dose Level - 1	Dose Level - 2	
Oxaliplatin	85 mg/m ²	70 mg/m ²	50 mg/m ²	
	Bolus 5-FU: 400 mg/m ²	Bolus 5-FU: 300 mg/m ²	Bolus 5-FU: 200 mg/m ²	
5-FU	Leucovorin: 400 mg/m ²	Leucovorin: 300 mg/m ²	Leucovorin: 200 mg/m ²	
	Infusion 5-FU: 2400 mg/m ² /48 hours	Infusion 5-FU: 2000 mg/m ² /48 hours	Infusion 5-FU: 1600 mg/m ² /48 hours	

5-FU: 5-fluorouracil

Table 4.6.2.3-2: Dose Modifications of FOLFOX

Toxicity	Definition	During a course of therapy	Dose adjustment for next treatments
			Dose level -1
Neutropenia	Grade 3 or greater	Interrupt until resolved to Grade 2	*If treatment delayed for 4 consecutive weeks, discontinue all treatment
			Dose level -1
	Grade 2	Interrupt until resolved to Grade 1	*If Grade 2 persists > 7 days, oxaliplatin reduced by 2 dose levels when platelets improve to Grade 1
			Dose level -1
Thrombocytopenia	Grade 3	Interrupt until resolved to Grade 1	*If Grade 3 persists > 7 days, oxaliplatin reduced by 2 dose levels when platelets improve to Grade 1
			Dose level -2
	Grade 4	Interrupt until resolved to Grade 1	*If Grade 4 persists > 7 days, oxaliplatin reduced by 2 dose levels when platelets improve to Grade 1
			Oxaliplatin dose -1
			Continue 5-FU and leucovorin
Neurologic toxicity	Grade 2 peripheral sensory neuropathy	Interrupt until resolved to Grade 1	*If oxaliplatin delayed for neurologic toxicity for 4 consecutive weeks, discontinue oxaliplatin, continue 5-FU and leucovorin
	Grade 3 or greater peripheral sensory neuropathy	Discontinue oxaliplatin	Continue 5-FU and leucovorin
			Dose level -1
Gastrointestinal toxicities	Grade 2 or greater diarrhea	Interrupt until resolved to Grade 1	If dose delayed for diarrhea for 4 consecutive weeks, discontinue all treatment

For toxicities not listed above, dose modifications are permitted per local standards.

Subjects may also discontinue oxaliplatin following multiple cycles if, in the investigator's judgment, cumulative toxicity is likely to increase over time and become problematic.

4.7 Criteria for Oxaliplatin-plus-Fluoropyrimidine Discontinuation

Except where specified below, both chemotherapy drugs in the platinum doublet chemotherapy regimen should be discontinued for any of the following:

- Any Grade \geq 4 peripheral neuropathy requires discontinuation of oxaliplatin.
- In case of persistent Grade 3 paraesthesia, oxaliplatin should be discontinued.

• Any Grade ≥ 3 mucocutaneous reaction possibly attributable to capecitabine or leucovorin requires permanent discontinuation.

- Grade \geq 3 drug-related thrombocytopenia associated with clinically significant bleeding
- Any drug-related liver function test (LFT) abnormality that meets the following criteria requires discontinuation:
 - AST or ALT > 5-10 x upper limit of normal (ULN) for > 2 weeks
 - AST or ALT $> 10 \times ULN$
 - Total bilirubin > 5 x ULN
 - Concurrent AST or ALT > 3 x ULN and total bilirubin > 2 x ULN
- Any oxaliplatin-related decrease in creatinine clearance to < 30 mL/min (using the Cockroft Gault formula) requires discontinuation of oxaliplatin.
- Any drug-related AE which recurs after 2 prior dose reductions for the same drug-related AE requires discontinuation of the drug(s) which was/were previously dose reduced.
- Any Grade ≥ 3 drug-related hypersensitivity reaction or infusion reaction requires discontinuation of the drug(s) felt to be causing the reaction. The drug not felt to be related to the hypersensitivity reaction or infusion reaction may be continued.
- Any Grade 4 drug-related AE which the investigator deems is inappropriate to be managed by dose reduction(s) requires discontinuation of the drug(s) felt to be causing the event. The drug not felt to be related to the event may be continued.
- If any toxicity does not resolve within 42 days, that component will be discontinued unless it is determined by the treating investigator that the subject might benefit from continuation of the component.

For toxicities that are not listed above, the treating investigators can decide to discontinue any individual chemotherapy agent or all chemotherapy agents if it is not the best interest in the subject per the local standards.

Post-treatment study follow-up is critically important and is essential to preserving subject safety and the integrity of the study. Subjects who discontinue study treatment will continue to be followed for collection of tumor surveillance assessments, safety, QoL questionnaires and biomarker sampling as per protocol.

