3.5 Discontinuation of Subjects following any Treatment with Study Drug

Subjects MUST discontinue investigational product (and non-investigational product at the discretion of the investigator) for any of the following reasons:

- Subject's request to stop study treatment
- Any clinical adverse event (AE), laboratory abnormality or intercurrent illness which, in the opinion of the investigator, indicates that continued participation in the study is not in the best interest of the subject
- Termination of the study by Bristol-Myers Squibb (BMS)
- Loss of ability to freely provide consent through imprisonment or involuntarily incarceration for treatment of either a psychiatric or physical (e.g., infectious disease) illness. (Note: Under specific circumstances and only in countries where local regulations permit, a participant who has been imprisoned may be permitted to continue as a participant. Strict conditions apply and BMS approval is required.)
- Toxicity as specified in Sections 4.5.1.5 and 4.7
- Disease progression assessed by RECIST 1.1 criteria, unless the subject meets criteria for treatment beyond progression.

In the case of pregnancy, the investigator must immediately notify the Sponsor or designee of this event. In most cases, the study drug will be permanently discontinued in an appropriate manner (e.g., dose tapering if necessary for subject safety). Please contact the Sponsor or designee within 24 hours of awareness of the pregnancy. If the investigator determines a possible favorable

benefit/risk ratio that warrants continuation of study drug, a discussion between the investigator and the Sponsor or designee must occur, if local regulations allow. If, for whatever reason, the pregnancy has ended, confirmed by negative serum pregnancy test, treatment may be resumed (at least 3 weeks and not greater than 6 weeks after the pregnancy has ended), following approvals of participant /sponsor /IRB/EC, as applicable.

All subjects who discontinue study drug should comply with protocol specified follow-up procedures as outlined in Section 5. The only exception to this requirement is when a subject withdraws consent for all study procedures including post-treatment study follow-up or loses the ability to consent freely (ie, is imprisoned or involuntarily incarcerated for the treatment of either a psychiatric or physical illness).

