4.5.2.2 Dose Modification Criteria for Nivolumab-plus-Chemotherapy

Dose modification criteria for the combination regimen should follow the respective individual dose modification criteria of each component. For chemotherapy, it is allowed to follow local standard or local package insert recommendations.

Dosing for all drugs should be delayed/interrupted if any criteria in Sections 4.5.1.2 (for nivolumab) or Sections 4.6.2.2 (for XELOX) and 4.6.2.3 (for FOLFOX.) are met.

Dose reduction of nivolumab are not permitted. Dose reduction for chemotherapy is permitted according to local standard or local package insert. See also Sections 4.6.2.2 for XELOX and 4.6.2.3 for FOLFOX.

Subjects may resume dosing when resuming criteria for BOTH nivolumab (Section 4.5.1.4) and chemotherapy (Section 4.6.2.2 for XELOX and Section 4.6.2.3 for FOLFOX) are met. That is, nivolumab and chemotherapy must be administered together until treatment discontinuation. It is allowed to administer either nivolumab or chemotherapy doublet or single drug alone if the other(s) are delayed or discontinued due to toxicity which is not overlapping for nivolumab and chemotherapy, judging by the treating investigator if it is the best interest in the subjects.

The assessments for discontinuation of nivolumab and/or chemotherapy should be made separately. Nivolumab discontinuation criteria are detailed in Section 4.5.1.5, and chemotherapy discontinuation criteria are detailed in Sections 4.6.2.2 (for XELOX) and 4.6.2.3 (for FOLFOX). Continuation of nivolumab alone when chemotherapy has been discontinued due to toxicity is permitted. Chemotherapy doublet or single drug is allowed to continue if the discontinuation criteria for nivolumab is met.

From Amendment 29, nivolumab 480 mg Q4W is permitted when all chemotherapy components are discontinued and nivolumab is continued alone. Subjects must be in the study for a minimum of 6 months from Cycle 1, Day 1 before switching to 480 mg Q4W nivolumab. Nivolumab 480 mg should be given 2 weeks or 3 weeks following the last administration of nivolumab 240 mg Q2W or 360 mg Q3W, respectively.

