4.6.2.2 Dose Modification Criteria for XELOX

Capecitabine

Toxicity due to capecitabine administration may be managed by symptomatic treatment and/or treatment interruption or dose reduction. Dose modifications of capecitabine are presented in Table 4.6.2.2-1. Once the dose has been reduced, it should not be increased at a later time. For those toxicities considered by the treating physician to be unlikely to become serious or life-threatening, eg alopecia, altered taste, or nail changes, treatment can be continued at the same dose without reduction or interruption. Subjects taking capecitabine should be informed of the need to interrupt treatment immediately if moderate or severe toxicity occurs. Doses of capecitabine omitted for toxicity are not replaced.

Approved v1000

Table 4.6.2.2-1: Recommended Dose Modifications of Capecitabine

Toxicity ^a	During a course of therapy	Dose adjuvant for next treatments (% of starting dose)
Grade 1	Maintain dose level	Maintain dose level
Grade 2		
1st appearance	Interrupt until resolved to	100% (1000 mg/m ²)
2nd appearance	Grade 0 1	75% (750 mg/m ²)
3rd appearance		50% (500 mg/m ²)
4th appearance	Discontinue treatment permanently	-
Grade 3		
1st appearance	Interrupt until resolved to	75% (750 mg/m ²)
2nd appearance	Grade 0 1	50% (500 mg/m ²)
3rd appearance	Discontinue treatment permanently	-
Grade 4		
1st appearance	Discontinue treatment permanently or,	50% (500 mg/m²)
	if physician deems it to be in the patient's best interest to continue, interrupt until resolved to Grade 0 - 1	

According to the National Cancer Institute of Canada Clinical Trial Group (NCIC CTG) Common Toxicity Criteria (version 1) or the Common Terminology Criteria for Adverse Events (CTCAE) of the Cancer Therapy Evaluation Program, US National Cancer Institute, version 4.0.

Oxaliplatin

Dose Modifications for Neurotoxicity

- For Grade 2 peripheral sensory neuropathy (moderate paresthesia or dysesthesia), or limiting instrumental activities of daily living, skip oxaliplatin. When toxicity resolves to ≤ Grade 1, resume oxaliplatin to 75% of initial dose. If oxaliplatin is skipped for 4 weeks (2 consecutive doses) for neurologic toxicity, discontinue oxaliplatin.
- For Grade 3 or greater peripheral sensory neuropathy (severe paresthesia or dysesthesia), or limiting self-care activities of daily living), discontinue oxaliplatin.

Dose Modifications for Subjects with Renal Impairment

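### For some Grade 3 neuropathy, Protocol Sections 4.6.2.2 and 4.6.2.3 require oxaliplatin to be stopped and Section 4.7 does not, and nothing says which prevails

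*Protocol*

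**What the plan says.** Three places in the protocol set a stopping rule for oxaliplatin in neuropathy.

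- **Section 4.6.2.2 (XELOX):** "For Grade 3 or greater peripheral sensory neuropathy (severe paresthesia or dysesthesia), or limiting self-care activities of daily living), discontinue oxaliplatin". No duration or persistence is attached.
- **Section 4.6.2.3 (FOLFOX), Table 4.6.2.3-2:** the row headed "Grade 3 or greater peripheral sensory neuropathy" stops oxaliplatin and keeps 5-FU and leucovorin going. Again there is no persistence condition.
- **Section 4.7 (discontinuation criteria):** "Any Grade \geq 4 peripheral neuropathy requires discontinuation of oxaliplatin". The next item reads: "In case of persistent Grade 3 paraesthesia, oxaliplatin should be discontinued". The section gives no duration that would make Grade 3 paraesthesia persistent.

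Section 4.7 also has a general item for unresolved toxicity: "If any toxicity does not resolve within 42 days, that component will be discontinued unless it is determined by the treating investigator". The exception, in short, is for cases where continuing is judged worthwhile.

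Two other sections tell the reader where to look. Section 3.5, which lists the reasons for which subjects must stop investigational product, includes "Toxicity as specified in Sections 4.5.1.5 and 4.7". Section 4.5.2.2, for the nivolumab-plus-chemotherapy arm, says that "chemotherapy discontinuation criteria are detailed in Sections 4.6.2.2 (for XELOX) and 4.6.2.3 (for FOLFOX"). It does not mention 4.7.

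**The concern.** A stopping rule for toxicity should have one reading. Here an investigator facing Grade 3 sensory neuropathy finds an unconditional stop in the regimen-specific section and a conditional one in the section titled as the discontinuation criteria.

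The toxicity is not a marginal one for this backbone. Protocol Section 1.1.1 names neuropathy, with renal toxicity, as a main reason for stopping platinum, and Section 1.1.11 gives it as a characteristic adverse event of platinum doublets. Oxaliplatin is in both arms of the primary comparison.

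Two things are at stake. The first is subject safety. The second is the meaning of the descriptive outputs that depend on when oxaliplatin stops: its relative dose intensity and cumulative dose (SAP Section 7.4.1, Tables 7.4.1-3 and 7.4.1-5) and adverse events leading to discontinuation (SAP Section 7.6.3). If sites followed different sections, part of the variation in these outputs reflects the section followed and not tolerability.

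**Working it through.** No arithmetic applies. The check is to set the rules side by side, then ask whether any other text settles the difference.

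**Step 1: do the sections cover the same toxicity?** Yes. Section 4.6.2.2 itself glosses its Grade 3 category as severe paresthesia or dysesthesia, which takes in the paraesthesia named in 4.7. Sensory neuropathy is also a form of peripheral neuropathy, so the Grade 4 item in 4.7 covers it.

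**Step 2: go through the cases.**

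| Case | 4.6.2.2 and 4.6.2.3 | Neuropathy items of 4.7 | Same result? |
|---|---|---|---|
| Grade 2 | Skip or interrupt; stop after four weeks off | No item | No immediate stop in either |
| Grade 3 paraesthesia, persistent | Stop | Stop | Yes |
| Grade 3, not persistent | Stop | Stop not required | **No** |
| Grade 3 dysesthesia without paraesthesia | Stop | No item, even if it lasts | **No** |
| Grade 4 | Stop | Stop | Yes |

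The rules part in two cases only, both at Grade 3.

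**Step 3: does the 42-day item in 4.7 close the gap?** No. It is not offered as the meaning of *persistent*. It says nothing about a Grade 3 event that resolves sooner. It also allows the investigator to keep the component, which the Grade 3 instructions in 4.6.2.2 and 4.6.2.3 do not.

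**Step 4: does any text set precedence?** None was found. The pointers lead to different places: Section 3.5 to 4.7, Section 4.5.2.2 to 4.6.2.2 and 4.6.2.3.

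**Step 5: could both sections be applied, stopping when either is met?** A site could do so without breaching anything. But the protocol does not say to, and for sensory neuropathy that reading would leave the Grade 4 threshold and the persistence condition in 4.7 with nothing to do.

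**The case against.** Four points can be made on the other side.

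*Section 4.7 never tells anyone to continue.* This stands. The section lists triggers for stopping and is silent on Grade 3 neuropathy that does not persist. A reader might infer that the sections give opposite orders, stop and continue. The documents do not support that. The conflict is between a stop that is required and a stop that is not, and a site that stops under 4.6.2.2 or 4.6.2.3 breaches nothing in 4.7.

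*Section 4.6.2 may be guidance, with 4.7 as the mandatory floor.* Sections 4.5.2.2, 4.6.2 and 4.6.2.1 allow chemotherapy modification by local standard, Section 4.6.2.3 introduces its tables as recommendations, and the Grade 4 item in 4.7 is worded as a requirement. This is a possible reading, but no text states it. The local-standard allowance concerns dose modification and does not say which stopping rule governs. The XELOX bullet is a direct instruction, and Section 4.5.2.2 describes 4.6.2.2 and 4.6.2.3 as holding the discontinuation criteria. The point weakens the contradiction without removing it.

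*Oxaliplatin exposure varies by design in any case.* Section 4.6.2.3 lets investigators stop oxaliplatin after several cycles if they foresee cumulative toxicity, and the 42-day item carries an investigator override. This stands in part. One clear rule would not make exposure uniform, so not all variation between sites can be put down to this wording.

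*The two arms could be stopped under different rules.* A reader might infer this, because the explicit pointer to 4.6.2.2 and 4.6.2.3 as discontinuation criteria is written for the nivolumab-plus-chemotherapy arm. The documents do not show it. Sections 4.6.2.2 and 4.6.2.3 sit under Section 4.6, which is the chemotherapy arm's dosing, so they bind the control arm too. Section 3.5, with its pointer to 4.7, covers all arms. A difference by arm is conjecture.

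**Conclusion.** The inconsistency is real. Sections 4.6.2.2 and 4.6.2.3 require oxaliplatin to stop for any sensory neuropathy of Grade 3 or above. Section 4.7 requires it only from Grade 4, or for Grade 3 paraesthesia that is persistent in an undefined sense. The protocol does not say which prevails.

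Its reach is limited. It touches Grade 3 events that do not persist and Grade 3 dysesthesia without paraesthesia, and it concerns oxaliplatin alone. The documents do not say how often such events were expected or occurred, so the effect on exposure and discontinuation summaries cannot be sized. No primary-endpoint definition, analysis population, alpha or power figure depends on it. Protocol Section 8.1.1 records that accrual ended in May 2019, before this protocol version of September 2019, so clarified wording could change care only for subjects still on oxaliplatin.

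The conclusion rests on reading the three sections as covering the same toxicity, which the gloss in 4.6.2.2 supports, and on there being no precedence statement in material outside the two documents. It takes no view on which rule is clinically right.

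**What to change.** Reconcile Sections 4.6.2.2, 4.6.2.3 and 4.7 so that a single stopping rule for Grade 3 neuropathy applies throughout and in both chemotherapy-containing arms. If the chosen rule depends on persistence, define it; state also whether dysesthesia is treated like paraesthesia. Align the pointers in Sections 3.5 and 4.5.2.2 so that both lead to the same criteria. The sponsor's clinical team decides the content of the rule.

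The cost is clarification wording in the protocol, with no change to sample size, analyses or data collection. For subjects already treated, a short descriptive table of Grade 3 sensory neuropathy by arm, showing whether oxaliplatin was stopped, would supply the missing frequency. It would draw on the adverse event grade and the action taken with study drug, which the SAP already uses.

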4.6.2.1 General Guidance for Dose Modification for Chemotherapy

- Treatment for the first cycle should only commence if all the inclusion criteria are met and the subject has been enrolled. For subsequent cycles, dose delay/modification is permitted per local standard or as described in Section 4.6.2.2 and Section 4.6.2.3.
- Doses of any study drug omitted for toxicity are not replaced or restored; instead, the patient should resume the planned treatment cycles. Supportive care (for example, colony-stimulating factors [CSFs], blood and blood products, etc. can be administered in accordance with the latest American Society of Clinical Oncology (ASCO) or other equivalent guidelines.
- Dose modification, for non-serious and non-life-threatening toxicities like alopecia, altered taste or nail changes may not be required and the final decision is left to the discretion of the treating investigator.
- In situations where concomitant toxicities of varying severity exist, dose modification will be tailored for the toxicity with highest CTCAE grading.
- If there is a delay or modification in administration of study drug(s) due to toxicity, treatment with the other study agent(s) should continue as scheduled. If clinically appropriate, the investigator can delay all treatment components up to a maximum of 7 days to allow synchronized administration of all agents.

If toxicity related to any component of chemotherapy does not resolve in the same treatment cycle, the administration of that component can be delayed up to 6 weeks. If the toxicity does not resolve within 6 weeks, that component will be discontinued unless it is determined by the treating investigator that the patient might benefit from continuation of the component.

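### Section 4.5.2.2 omits Section 4.7 from its chemotherapy discontinuation pointer, so nivolumab-plus-chemotherapy sites can reach a capecitabine re-dosing rule for reactions that Section 4.7 says must stop treatment

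*Protocol*

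**What the plan says.** Four parts of the Protocol bear on this.

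- **Section 3.5** lists the reasons for which subjects must discontinue investigational product. Toxicity as set out in Sections 4.5.1.5 and 4.7 is one of them. Section 4.1 counts capecitabine, oxaliplatin, fluorouracil and leucovorin as investigational products.
- **Section 4.7** opens with "Except where specified below, both chemotherapy drugs in the platinum doublet chemotherapy regimen should be discontinued for any of the following". One of its bullets reads "Any Grade ≥ 3 mucocutaneous reaction possibly attributable to capecitabine or leucovorin requires permanent discontinuation". That bullet offers no resumption and no investigator discretion.
- **Section 4.6.2.2** says "Toxicity due to capecitabine administration may be managed by symptomatic treatment and/or treatment interruption or dose reduction". Table 4.6.2.2-1, headed as recommended modifications, then sets the action by grade and number of appearances. Type of toxicity matters only in a permissive sentence about events such as alopecia. Section 4.7 is not mentioned.
- **Section 4.5.2.2**, for the nivolumab-plus-chemotherapy arm, says that "chemotherapy discontinuation criteria are detailed in Sections 4.6.2.2 (for XELOX) and 4.6.2.3 (for FOLFOX"). Section 4.7 is not mentioned there either.

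**The concern.** Section 4.5.2.2 is where staff treating a nivolumab-plus-chemotherapy patient would look to learn when chemotherapy must stop. It sends them to two sections on dose modification and past the section written for discontinuation. On the XELOX side they arrive at a table that permits further capecitabine after Grade 3 or 4 toxicity, including reactions for which Section 4.7 permits none.

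What is at stake is whether a patient with a severe mucocutaneous reaction is given the suspected drug again. The question is whether treatment stops or resumes. It does not bear on the efficacy analyses.

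**Working it through.** No formula in the plan applies to the main point, so the check sets the texts side by side.

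**Step 1: the same event under the two rules.** Take a mucocutaneous reaction possibly attributable to capecitabine.

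| Event | Table 4.6.2.2-1 | Section 4.7 |
|---|---|---|
| Grade 3, first | Interrupt to Grade 0–1, resume at 75% (750 mg/m²) | Stop permanently |
| Grade 3, second | Interrupt to Grade 0–1, resume at 50% (500 mg/m²) | Not reached: stopped at the first |
| Grade 3, third | Stop permanently | Not reached |
| Grade 4, first | Stop permanently or, if the physician judges it in the patient's "best interest to continue, interrupt until resolved to Grade 0 - 1", then 50% (500 mg/m²) | Stop permanently |

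The actions differ at the first Grade 3 event, and at Grade 4 if the physician uses the discretion.

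**Step 2: which rule governs.** Section 3.5 is mandatory, applies to all subjects and cites 4.7. The table is a recommendation. Read together, 4.7 prevails.

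**Step 3: where the pointer leads.**
- XELOX: to the table in Step 1.
- FOLFOX: to Section 4.6.2.3, which has no mucocutaneous row and ends with "For toxicities not listed above, dose modifications are permitted per local standards". This is silence plus a permission. It does not contradict 4.7, but it does not lead the reader there.

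**Step 4: other stops bypassed.** Section 4.7 also has liver-test thresholds (for example AST or ALT above 10 × ULN, or total bilirubin above 5 × ULN) and stops for Grade 3 or higher thrombocytopenia with clinically significant bleeding and for Grade 3 or higher hypersensitivity. None of these appears in 4.6.2.2 or 4.6.2.3. The gap is therefore the missing reference to 4.7 as a whole.

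**Step 5: comparison within the protocol.** For nivolumab and ipilimumab, the resumption rules in Section 4.5.1.4 defer explicitly to the discontinuation rules in 4.5.1.5. The chemotherapy sections have no such link.

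**Step 6: reach.** Accrual ended in May 2019 (Section 8.1.1), and this version is dated 16-Sep-2019. From 31 May that is 108 days, 108/30.4375 = 3.5 months. From 1 May it is 138 days, 138/30.4375 = 4.5 months. Using the chemotherapy PFS hazards in Table 8.1.4-1 (0.09 per month to month 3, then 0.17):
- S(3.5) = exp(−(0.09 × 3 + 0.17 × 0.5)) = exp(−0.355) = 70%
- S(4.5) = exp(−(0.09 × 3 + 0.17 × 1.5)) = exp(−0.525) = 59%

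The plan's 6-month-delay scenario gives the nivolumab-plus-chemotherapy arm the same values, because its hazard ratio is 1 over this period. So perhaps 59% to 70% of subjects randomized in May 2019 would be expected to be progression-free at this version's date. This applies only to the last subjects randomized. It does not count those on chemotherapy, since some stop for other reasons. It shows only that the affected group need not be empty.

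**The case against.** The strongest reply is that the protocol already gives the right answer. Section 3.5 makes 4.7 mandatory in every arm, 4.7 follows directly after the dose-modification sections, and the table is only recommended. A general grade table followed by a specific stop list is a normal structure. The two also fit together elsewhere. Section 4.7 stops a drug when an event recurs after two reductions, which matches the table's 75%, 50%, stop sequence, and it leaves other Grade 4 events to judgment about dose reduction, as the table does. The pointer is incomplete but not false, since 4.6.2.2 and 4.6.2.3 do contain some discontinuation rules.

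Most of this stands. A reader might infer that the capecitabine table is wrong as written, or that the protocol leaves the governing rule open. The documents support neither. The reply does not cure the pointer, however. Section 4.5.2.2 says where the discontinuation criteria are and leaves out the section that holds the mandatory ones. Reaching the safe action then depends on the reader consulting 3.5 or 4.7 unprompted.

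A reader might also infer that oxaliplatin must stop for the same reaction, because the 4.7 lead-in refers to both drugs and this bullet states no exception. That is one reading. The bullet names suspected causes but not which drug stops, several neighbouring bullets stop only the causative drug, and Section 4.6.2.1 says that when one drug is delayed or modified, "treatment with the other study agent(s) should continue as scheduled". The text does not settle it.

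**Conclusion.** The point holds as a minor patient-safety consistency correction. The operative pointer for the nivolumab-plus-chemotherapy arm omits the mandatory discontinuation section. A XELOX site that follows it reaches a table allowing capecitabine at 75% or 50% after Grade 3, or at 50% by discretion after Grade 4, for reactions that 4.7 says end treatment. The other 4.7 stops are bypassed in the same way.

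Its size cannot be put as a number of patients. The documents give no incidence and do not define a mucocutaneous reaction, so the share of capecitabine skin or mucosal events covered is unknown. Reach is limited to subjects still on chemotherapy after 16-Sep-2019. The conclusion assumes that a site may act on the sections 4.5.2.2 names without also consulting 3.5 or 4.7; the documents do not show that any site did so. There is no effect on PFS, OS, power or alpha.

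**What to change.** 1. In Section 4.5.2.2, add Section 4.7 to the chemotherapy discontinuation pointer, alongside 4.6.2.2 and 4.6.2.3. This covers FOLFOX sites as well.
2. Add a note to Table 4.6.2.2-1 that the discontinuation criteria in Section 4.7, including those for Grade 3 or higher mucocutaneous reactions possibly attributable to capecitabine, take precedence over the grade-based resumption rules. Wording it as 4.7 in general, with this reaction as the named example, avoids leaving the liver-test and other stops unflagged.
3. Confine that note to the capecitabine table. Section 4.6.2.2 is stricter than 4.7 on oxaliplatin neuropathy: "For Grade 3 or greater peripheral sensory neuropathy (severe paresthesia or dysesthesia), or limiting self-care activities of daily living), discontinue oxaliplatin". Section 4.7 instead stops oxaliplatin at Grade 4 neuropathy or persistent Grade 3 paraesthesia. A blanket precedence statement would loosen the stricter rule.

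The cost is one cross-reference and one table note, by administrative letter or in the next amendment, with a short memo to sites. No procedures, visits or patients are added.
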